#### **12.1.6. Subgroup Analyses for Randomized Subjects**

Primary and pre-specified additional endpoints will be summarized and treatment groups will be compared for the following subgroups of randomized subjects.

- Gender (male and female)
- Extreme risk and high risk (see Table 26.2-1 for definitions of extreme and high operative risk)
- Region (North America, outside North America)

No adjustments for multiple comparisons will be made. Additional analyses may be performed as appropriate.

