#### *12.1.2.2.2 Secondary Hypothesis*

The sample size calculation for the secondary hypothesis of the primary effectiveness endpoint at 1 year is based on the following assumptions.

- Expected Lotus Valve (test) rate = 22%
- Expected CoreValve (control) rate = 32%
- Test significance level ( $\alpha$ ) = 0.05 (2-sided)
- Test : Control ratio = 2:1
- Expected rate of attrition = 10%

Given enrollment of 912 subjects (608 Lotus Valve, 304 CoreValve) and 10% attrition, there is approximately 86% power to show superiority with the given expected rates.

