#### **12.1.5. Post-procedure Measurements**

Post-procedure information will be collected at regularly scheduled follow-up examinations as detailed in the clinical study schedule (Table 11.1-1) and will be summarized using descriptive statistics for continuous variables (e.g., mean, standard deviation, n, minimum, maximum) and frequency tables or proportions for discrete variables. Estimates will be reported by treatment group and, for randomized subjects, differences between treatment groups and their 95% confidence intervals will be presented. Treatments for the randomized subjects will be compared with the chi-square or Fisher exact test for discrete variables and the Student t-test for continuous variables. No inferences are planned on the additional measurements and, therefore, alpha-adjustments for multiple comparisons will not be used. The Kaplan-Meier product-limit method will be used to estimate rates for time-to-event endpoints and treatment groups will be compared using the Log-rank and Wilcoxon tests. Adverse event and SAE rates will be reported. No formal statistical testing will be done for the roll-in (with the 23 mm, 25 mm, or 27 mm Lotus Valve), Lotus 21 mm Nested Registry, LOTUS Edge Nested Registry, roll-in with the 29 mm LOTUS Edge Valve, LOTUS Edge 29 mm Nested Registry, or U.S. Continued Access Study subjects.

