### 12.3.3. Justification of Pooling

Analyses for the primary safety and effectiveness endpoints and the secondary endpoint will be presented using data pooled across institutions and surgical (high or extreme) risk groups. An assessment of the poolability of subjects across centers and surgical risk groups will be made using logistic regression. Main effects for the center (risk group) and treatment and the interaction of the center (risk group) by treatment will be included in separate logistic regression models with the primary safety endpoint, the primary effectiveness endpoint, and the secondary endpoint as the outcome. If the  $P$  value for center (risk group) by treatment interaction is  $\geq 0.15$ , it can be concluded that the treatment effect is not different across the centers (risk groups) and the data can be pooled. In the analysis to justify pooling across centers, the centers with fewer than 6 subjects enrolled in the study will be combined into “virtual centers” based on geographic region so that “virtual centers” have  $\geq 6$  subjects but no more than the largest enrolling center.

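### Sex and region subgroups are to be compared arm against arm within each level, with no stated interaction test to show whether the effect differs between levels

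*Combined protocol and SAP*

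**What the plan says.** Section 12.1.6 sets out the subgroup method for the randomized cohort: "Primary and pre-specified additional endpoints will be summarized and treatment groups will be compared for the following subgroups of randomized subjects". The factors are sex, extreme versus high operative risk, and region (North America versus elsewhere). The section adds: "No adjustments for multiple comparisons will be made". It names no test and no treatment-by-subgroup interaction, and leaves further analyses open.

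Section 12.1.5 describes how post-procedure outcomes are compared: "Treatments for the randomized subjects will be compared with the chi-square or Fisher exact test for discrete variables". It also provides for treatment differences with 95% confidence intervals.

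Interaction models appear only in section 12.3.3, as a check on pooling: "Main effects for the center (risk group) and treatment and the interaction of the center (risk group) by treatment will be included". They are separate logistic regressions for the two primary endpoints and the secondary endpoint, and pooling is accepted if the interaction P value is at least 0.15. Section 12.3.4 mentions univariate and multivariate predictor analyses without naming an interaction with sex or region.

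**The concern.** A subgroup analysis should show whether the treatment effect differs between levels of a factor. A test inside each level answers another question: whether the data in that level alone exclude no effect. The answer depends heavily on how many subjects are in the level. Two levels with the same true effect can easily fall on different sides of P=0.05 because each holds only part of the sample.

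Operative risk has a direct check in section 12.3.3. Sex and region do not. If one sex, or one region, is significant and the other is not, nothing else specified for that factor tells a reader whether the two effects differ by more than chance.

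**Working it through.** **Inputs.** Section 12.1.2.2.2 gives Lotus 22%, CoreValve 32%, two-sided alpha 0.05, 2:1 allocation, 912 randomized, 10% attrition and about 86% power. Evaluable: 912 × 0.9 = 820.8, or 547.2 Lotus and 273.6 CoreValve.

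**Formula.** Power of the chi-square test by the normal approximation, with d the difference in rates:

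- power = Φ[(d − 1.96 × SE0) / SE1]
- SE0 = √[p̄(1 − p̄)(1/nT + 1/nC)], where p̄ is the pooled rate
- SE1 = √[pT(1 − pT)/nT + pC(1 − pC)/nC]

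**The plan's own figure.** p̄ = (2 × 0.22 + 0.32)/3 = 0.2533; SE0 = 0.03220; SE1 = 0.03330. Power = Φ[(0.10 − 0.0631)/0.03330] = Φ(1.107) = 86.6%, against the stated 86%. The method matches the sponsor's.

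**One half of the trial.** The documents give no split for sex or region, so an equal split is an assumption. With 273.6 Lotus and 136.8 CoreValve, SE0 = 0.04554 and SE1 = 0.04709. Power = Φ[(0.10 − 0.0893)/0.04709] = Φ(0.228) = 59.0%.

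**Exactly one level significant, same true effect in both.** The levels are independent, so the chance is p1(1 − p2) + p2(1 − p1). For equal halves this is 2 × 0.590 × 0.410 = 48.4%. A simulation of 200,000 trials gives 48.5%.

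**Uneven splits at 22% vs 32%:**

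| Split | Power, larger level | Power, smaller level | Exactly one significant |
|---|---|---|---|
| 50:50 | 59% | 59% | 48% |
| 60:40 | 67% | 50% | 50% |
| 70:30 | 73% | 40% | 55% |
| 80:20 | 79% | 29% | 62% |

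**Other true effects, equal split, control 32%, significance counted in either direction:**

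| True Lotus rate | Power per half | Exactly one significant |
|---|---|---|
| 22% | 59.0% | 48% |
| 25% | 32.7% | 44% |
| 27% | 18.8% | 31% |
| 29% | 9.8% | 18% |
| 32% (no effect) | 5.0% | 9.5% |

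**What an interaction test would do.** In the equal-split, equal-effect case at 22% vs 32%, a test of the difference between the two risk differences rejected in 5.1% of simulated trials at the 0.05 level, close to nominal.

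**Its power when effects do differ.** Take a 15-point benefit in one half and a 5-point benefit in the other: Lotus 17% and 27%, control 32% in both.

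- Variance, first half: 0.17 × 0.83/273.6 + 0.32 × 0.68/136.8 = 0.002106
- Variance, second half: 0.27 × 0.73/273.6 + 0.32 × 0.68/136.8 = 0.002311
- SE of the difference: √0.004417 = 0.0665
- Power: Φ(0.10/0.0665 − 1.96) = Φ(−0.455) = about 32%

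**The case against.** Section 12.1.6 sets no alpha and no success rule for subgroups. Formal claims are confined to the three-step hierarchy in section 12.1, which contains no subgroup, and section 12.1.5 disclaims inference on the additional measurements. A reader might infer that the plan licenses a claim that the device works in one sex and not the other. It does not; that would be misuse of the output. This limits the consequences, but section 12.1.5 plans chi-square or Fisher comparisons, so within-level P values are likely to be produced, with nothing beside them to test a difference.

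The 48% rests on the superiority alternative, which is the last step of the hierarchy. The primary effectiveness hypothesis assumes 32% in both arms (section 12.1.2.2.1), where the superiority-test figure is 9.5%. This stands, and the range above has to travel with the headline number. Section 12.1.6 does not say whether the non-inferiority margins would be reused within subgroups, so no figure is claimed for that case.

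Several sections defer detail to a Statistical Analysis Plan. The accurate statement is therefore that no sex or region interaction is stated in the supplied documents, not that none exists anywhere.

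An interaction test is also weak at this sample size, as the 32% shows. That is a reason for caution in reading it, not for relying on separate tests, which do not address the question.

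**Conclusion.** The point holds for sex and region. The stated method does not show whether the treatment effect differs between levels, and the supplied documents specify nothing else that does. With identical true effects, the chance of exactly one significant level is about 48% under two assumptions: the superiority effect is true and the split is equal. It is 50% to 62% for splits from 60:40 to 80:20. With an equal split it is lower for smaller effects, down to 9.5% with none.

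Four stronger readings are tempting and not supported:

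- That discordant results would arise about half the time whatever the truth. The figure depends on the true effect and on a split that the documents do not give.
- That discordance means effects in opposite directions. It means only that one level is significant and the other is not.
- That operative risk shares the gap. Section 12.3.3 already fits its interaction for both primary endpoints and the secondary endpoint.
- That the region factor sets U.S. against non-U.S. results, or that device labelling turns on it. The factor is North America versus elsewhere, Canada is a participating country, and the documents say nothing of labelling by subgroup.

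No primary or secondary conclusion changes.

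**What to change.** Add a treatment-by-sex model and a treatment-by-region model, fitted separately, to the logistic regressions already planned in section 12.3.3 for the two primary endpoints and the secondary endpoint. State that the interaction is on the odds-ratio scale, or use a risk-difference model if that is the reporting scale. The choice matters because equal risk differences at different baseline risks give unequal odds ratios. In section 12.1.6, report the interaction P value with subgroup risk differences and 95% CIs, and label all subgroup analyses exploratory, including any within-subgroup P values that are kept.

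The cost is a few sentences and a little programming; section 12.3.5 allows an amended SAP before the analyses are run. The main downside is low power: with about 32% for a 15-point versus 5-point benefit in equal halves, a non-significant interaction must not be read as proof of a uniform effect, and the text should say so. The secondary endpoint will be sparse. At the design rates the Lotus arm would have about 608 × 0.75 × 0.011 = 5 events, so its interaction estimate may be unstable.

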#### **12.1.7. Subgroup Analyses for U.S. Continued Access Study Subjects**

Primary and pre-specified additional endpoints will be summarized and treatment groups will be compared for the following subgroups of U.S. Continued Access Study subjects.

- Gender (male and female)
- Extreme risk and high risk (see Table 26.2-1 for definitions of extreme and high operative risk)

No adjustments for multiple comparisons will be made. Additional analyses may be performed as appropriate.

## 12.2. *General Statistical Methods*

All statistical analyses will be performed using the SAS System software, version 9.2 or later (Copyright© 2000 SAS Institute Inc., [name]. All rights reserved).

All statistical analyses will be conducted according to applicable Standard Operating Procedures, Work Instructions, and the study-specific Statistical Analysis Plan.

### 12.2.1. Analysis Sets

The primary endpoints and additional measurements will be analyzed on an ITT, an as-treated, and an implanted basis. Among the randomized cohort, for ITT analyses, all subjects who sign the IRB/IEC-approved study ICF (see Section 11.3), are enrolled in the trial, and are randomized will be included in the analysis, whether or not an assigned study valve (Lotus Valve or CoreValve) was implanted. The as-treated population includes all subjects who sign the IRB/IEC-approved study ICF, are enrolled in the trial, and are randomized, with the analysis based on the treatment actually received (for example, if a subject is assigned to receive a test device but instead receives a control device, that subject will be considered a control subject for the as-treated analyses). For implanted analyses, ITT subjects who had the assigned, randomized study valve (Lotus Valve or CoreValve) implanted will be included in the analysis. For all analysis sets, if a subject receives 2 valves, the subject is assigned to the group corresponding to the first valve received. Among the roll-in (with the 23 mm, 25 mm, or 27 mm Lotus Valve), Lotus 21 mm Nested Registry, LOTUS Edge Nested Registry, roll-in with the 29 mm LOTUS Edge Valve, LOTUS Edge 29 mm Nested Registry, and U.S. Continued Access Study cohorts, for ITT analyses, all subjects who sign the IRB/IEC-approved study ICF and are enrolled in the trial will be included in the analysis sample, regardless of whether the study device was implanted. For these cohorts, the as-treated population includes all subjects implanted with the Lotus Valve. The as-treated and implanted analysis sets are the same for these cohorts.

For the randomized cohort, the primary safety endpoint, primary effectiveness endpoint (both hypotheses), and the secondary endpoint will all be analyzed for the ITT, as-treated, and implanted analysis sets. The primary analysis for the primary hypothesis of the primary effectiveness endpoint and the primary safety endpoint will be based on the implanted analysis set. The primary analysis set for the secondary hypothesis of the primary effectiveness endpoint and the secondary endpoint will be based on the ITT analysis set.

After 1 year, all analyses will be based on the safety analysis set. All subjects who sign the written ICF, are enrolled in the study, and have a study device implanted regardless of the device and treatment assignment will be included in the safety analysis set.

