	
implantation.
 
EC26. Subject has severe incapacitating dementia.
 
Additional exclusion criteria apply for subjects considered for enrollment in the CT Imaging substudy of the U.S. Continued Access Study as listed below.
 
AEC1. Subject has eGFR <30 mL/min (chronic kidney disease stage IV or stage V).
 
AEC2. Subject has atrial fibrillation that cannot be rate controlled to ventricular response rate < 60 bpm.
 
AEC3. Subject is expected to undergo chronic anticoagulation therapy after the TAVR procedure.
 
Note: Subjects treated with short-term anticoagulation post-procedure can be included in the imaging substudy; in these subjects the 30-day imaging will be performed 30 days after discontinuation of anticoagulation.

Statistical Methods	
Analysis Sets	
Analysis sets for the randomized cohort are listed below.
 
As-Treated: This population includes all subjects who sign an Informed Consent Form, are enrolled in the trial, are randomized, and received a study device, but is based on the treatment actually received.
 
Intention-To-Treat (ITT): This population includes all subjects who sign an Informed Consent Form, are enrolled in the trial, and are randomized, whether or not an assigned study device is implanted.
 
Implanted: This population includes all subjects who sign an Informed Consent Form, are enrolled in the trial, and are implanted with the assigned, randomized study device.
 
For all randomized cohort analysis sets, if a subject receives 2 valves, the subject is assigned to the group corresponding to the first valve received.
 
Among the roll-in (initial cohort with the 23, 25 and 27 mm Lotus), Lotus 21 mm Nested Registry, LOTUS Edge Nested Registry, roll-in with the 29 mm LOTUS Edge, LOTUS Edge 29 mm Nested Registry, and U.S. Continued Access cohorts, for ITT analyses all subjects who sign an Informed Consent Form and are enrolled in the study will be included in the analysis sample, regardless of whether the study device was implanted. The As-Treated population is the same as the Implanted population for these cohorts and includes all subjects who sign an Informed Consent Form

REPRISE III: REpositionable Percutaneous Replacement of Stenotic Aortic Valve through Implantation of Lotus™ Valve System – Randomized Clinical Evaluation	
	and are implanted with the Lotus Valve.

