Primary Safety Endpoint Statistical Hypothesis	The primary safety endpoint (composite of all-cause mortality, stroke, life-threatening and major bleeding events, stage 2 or 3 acute kidney injury, or major vascular complications at 30 days) rate for the Lotus Valve is non-inferior to that for CoreValve.
Statistical Test Method for the Primary Safety Endpoint	
A Farrington-Manning standardized test will be used to test the one-sided hypothesis of non-inferiority of the Lotus Valve versus CoreValve:
 
<math>H_0: P_{S\_Lotus} \text{ minus } P_{S\_Control} \geq \Delta</math> (Inferior)
 
<math>H_1: P_{S\_Lotus} \text{ minus } P_{S\_Control} < \Delta</math> (Non-inferior)
 
where <math>P_{S\_Lotus}</math> and <math>P_{S\_Control}</math> are the rates of the primary safety endpoint for the Lotus Valve group (test) and the CoreValve group (control), respectively, and <math>\Delta</math> (delta) is the non-inferiority margin.
 
The primary analysis set for the primary safety endpoint is the implanted analysis set. This endpoint will also be analyzed for the ITT and as-treated analysis sets.

Sample Size Parameters for the Primary Safety Endpoint	
 
• Expected Lotus Valve (test) rate = 40%
 
• Expected CoreValve (control) rate = 40%
 
• Non-inferiority margin (<math>\Delta</math>) = 10.5%
 
• Test significance level (<math>\alpha</math>) = 0.025 (1-sided)
 
• Test : Control ratio = 2:1
 
• Expected rate of attrition = 5%
 
• Given enrollment of 912 subjects (608 Lotus Valve, 304 CoreValve) and 5% attrition, there is approximately 85% power to show non-inferiority with the given expected rates
 

Success Criteria for the Primary Safety Endpoint	If the $P$ value from the Farrington-Manning standardized test is $<0.025$ , the rate of the primary safety endpoint for the Lotus Valve will be concluded to be non-inferior to the CoreValve rate. This corresponds to the one-sided upper 97.5% confidence bound on the difference between treatment groups (Lotus Valve minus CoreValve) for the observed rate of the primary safety endpoint being less than delta.
Primary Effectiveness	The primary effectiveness endpoint (composite of all-cause mortality, disabling stroke, or moderate or greater paravalvular aortic regurgitation

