REPRISE III: REpositionable Percutaneous Replacement of Stenotic Aortic Valve through Implantation of Lotus™ Valve System – Randomized Clinical Evaluation	
Endpoint Statistical Hypothesis	[based on core lab assessment] at 1 year) rate for the Lotus Valve group is noninferior to that for the CoreValve group. If non-inferiority is shown for the Lotus group for the primary safety and primary effectiveness endpoints, superiority is shown for the secondary endpoint, and the rate for the Lotus group is less than the rate for the CoreValve group for the primary effectiveness endpoint, then a test of superiority will be performed for the primary effectiveness endpoint.
Statistical Test Method for the Primary Effectiveness Endpoint – Non-Inferiority	
A Farrington-Manning standardized test will be used to test the one-sided hypothesis of non-inferiority of the Lotus Valve versus CoreValve:
 
<math>H_0: P_{E\_Lotus} \text{ minus } P_{E\_Control} \geq \Delta</math> (Inferior)
 
<math>H_1: P_{E\_Lotus} \text{ minus } P_{E\_Control} < \Delta</math> (Non-inferior)
 
where <math>P_{E\_Lotus}</math> and <math>P_{E\_Control}</math> correspond to the rates of the primary effectiveness endpoint for the Lotus Valve group (test) and the CoreValve group (control), respectively.
 
The primary analysis set for the primary effectiveness endpoint is the implanted analysis set. This endpoint will also be analyzed for the ITT and as-treated analysis sets.

Sample Size Parameters for the Primary Effectiveness Endpoint – Non-Inferiority	
 
• Expected Lotus Valve (test) rate <math>P_{E\_Lotus} = 32\%</math>
 
• Expected CoreValve (control) rate <math>P_{E\_Control} = 32\%</math>
 
• Non-inferiority margin (<math>\Delta</math>) = 9.5%
 
• Test significance level (<math>\alpha</math>) = 0.025 (1-sided)
 
• Test : Control ratio = 2:1
 
• Power (<math>1-\beta</math>) = 80%
 
• Total number of evaluable subjects = 819
 
• Expected rate of attrition = 10%
 
 
N = 912 subjects (608 Lotus Valve, 304 CoreValve)

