Success Criteria for the Primary Effectiveness Endpoint – Non-Inferiority	If the P value from the Farrington-Manning standardized test is <0.025, the rate of the primary effectiveness endpoint for the Lotus Valve will be concluded to be non-inferior to the CoreValve rate. This corresponds to the one-sided upper 97.5% confidence bound on the difference between treatment groups (Lotus Valve minus CoreValve) for the observed rate of the primary effectiveness endpoint being less than delta.

REPRISE III: REpositionable Percutaneous Replacement of Stenotic Aortic Valve through Implantation of Lotus™ Valve System – Randomized Clinical Evaluation	
Statistical Test Method for the Primary Effectiveness Endpoint – Superiority	
A chi-square test will be used to test the two-sided hypothesis of superiority of the Lotus Valve versus CoreValve:
 $H_0: P_{E\_Lotus} = P_{E\_Control}$ $H_1: P_{E\_Lotus} \neq P_{E\_Control}$ 
where <math>P_{E\_Lotus}</math> and <math>P_{E\_Control}</math> correspond to the rates of the primary effectiveness endpoint for the Lotus Valve group (test) and the CoreValve group (control), respectively.
 
The primary analysis set for superiority test of the primary effectiveness endpoint is the ITT analysis set. This endpoint will also be analyzed for the as-treated and implanted analysis sets.

Sample Size Parameters for the Primary Effectiveness Endpoint – Superiority	
 
• Expected Lotus Valve (test) rate <math>P_{E\_Lotus} = 22\%</math>
 
• Expected CoreValve (control) rate <math>P_{E\_Control} = 32\%</math>
 
• Test significance level (<math>\alpha</math>) = 0.05 (2-sided)
 
• Test : Control ratio = 2:1
 
• Power (<math>1-\beta</math>) = 80%
 
• Total number of evaluable subjects = 684
 
• Expected rate of attrition = 10%
 
• Given enrollment of 912 subjects (608 Lotus Valve, 304 CoreValve) and 10% attrition, there is approximately 86% power to show superiority with the given expected rates
 

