HOSTILE CHEST	
Any of the following or other reasons that make redo operation through sternotomy or right anterior thoracotomy prohibitively hazardous:
 
 
● Abnormal chest wall anatomy due to severe kyphoscoliosis or other skeletal abnormalities (including thoracoplasty, Potts' disease)
 
● Complications from prior surgery
 
● Evidence of severe radiation damage (e.g. skin burns, bone destruction, muscle loss, lung fibrosis or esophageal stricture)
 
● History of multiple recurrent pleural effusions causing internal adhesions
 

IMPLANTED ANALYSIS SET	
This population includes all subjects who sign an Informed Consent Form, are enrolled in the trial, and are implanted with the assigned, randomized study device.
 
Note 1: If a subject receives 2 valves, the subject is assigned to the group corresponding to the first valve received.

INTENT TO TREAT (ITT) ANALYSIS SET	
This population includes all subjects who sign an Informed Consent Form, are enrolled in the trial, and are randomized, whether or not an assigned study device is implanted. Subjects in the ITT population will be followed with their ITT cohort.
 
Note 1: If a subject receives 2 valves, the subject is assigned to the group

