**Table 26.2-1: Definitions**

Term	Definition
	corresponding to the first valve received.
INTERNAL MAMMARY ARTERY OR OTHER CRITICAL CONDUIT(S) CROSSING MIDLINE AND/OR ADHERENT TO POSTERIOR TABLE OF STERNUM	
A patent IMA graft that is adherent to the sternum such that injuring it during reoperation is likely. A patient may be considered extreme risk if any of the following are present:
 
 
• The conduit(s) are radiographically indistinguishable from the posterior table of the sternum.
 
• The conduit(s) are radiographically distinguishable from the posterior table of the sternum but lie within 2-3mm of the posterior table.
 

INTRACRANIAL HEMORRHAGE	Collection of blood between the brain and skull; subcategorized as epidural, subdural, and subarachnoid bleeds.
LEFT BUNDLE BRANCH BLOCK (LBBB)	
The appearance of typical complete LBBB in the three KEY leads (I, V1, and V6) with the following diagnostic criteria [see Figure below].
 
 
• The heart rhythm must be supraventricular in origin
 
• QRS widening to at least 0.12 sec
 
• An upright (monophasic) QRS complex in leads I and V6; the QRS may be notched, but there should not be any q wave in either lead I or lead V6.
 
• A predominantly negative QRS complex in lead V1; there may or may not be an initial small r wave in lead V1, that is, lead V1 may show either a QS or RS complex.
 
 
LIVER DISEASE (SEVERE) /CIRRHOSIS	
Any of the following:
 
 
• Child-Pugh class C
 
• MELD score <math>\geq 10</math>
 
• Portal-caval, spleno-renal, or transjugular intrahepatic portal shunt
 
• Biopsy proven cirrhosis with portal hypertension or hepatocellular dysfunction
 

MITRAL VALVE APPARATUS DAMAGE	Angiographic or echocardiographic evidence of a new damage to the mitral valve apparatus (chordae papillary muscle, or leaflet) during or after the TAVR procedure.
MODIFIED DEVICE SUCCESS	Absence of mortality with the originally implanted transcatheter valve in the proper anatomical location, no additional aortic valve procedures, and with the intended performance of the prosthetic valve (either a mean aortic valve gradient $< 20$ mm Hg or a peak velocity $< 3$ m/sec with no moderate or severe prosthetic valve aortic regurgitation)

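### The rule that places two-valve subjects in the group of the first valve received is applied to the ITT set, where it contradicts analysis by randomised arm

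*Combined protocol and SAP*

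**What the plan says.** The synopsis (Analysis Sets) defines the as-treated, ITT and Implanted sets and then adds: "For all randomized cohort analysis sets, if a subject receives 2 valves, the subject is assigned to the group corresponding to the first valve received". Section 7 states the same rule for all analysis sets, and Section 12.2.1 again says: "For all analysis sets, if a subject receives 2 valves, the subject is assigned to the group corresponding to the first valve received".

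In Table 26.2-1 the ITT entry covers every randomised subject, whether or not an assigned device was implanted. It says: "Subjects in the ITT population will be followed with their ITT cohort". Note 1 of that same entry then puts a two-valve subject in the group "corresponding to the first valve received".

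The deciding sets differ by test:

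- **Non-inferiority.** In the synopsis, for safety: "The primary analysis set for the primary safety endpoint is the implanted analysis set". For effectiveness: "The primary analysis set for the primary effectiveness endpoint is the implanted analysis set". Section 12.2.1 agrees that the analysis of the "primary effectiveness endpoint and the primary safety endpoint will be based on the implanted analysis set".
- **Superiority.** "The primary analysis set for superiority test of the primary effectiveness endpoint is the ITT analysis set". The synopsis and Sections 7.1.3 and 12.2.1 also make ITT the primary set for the secondary endpoint.

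**The concern.** An ITT comparison is protected because arm membership is fixed at randomisation. The first valve received is known only after randomisation and depends on what happens in the procedure. Using it to define the arm lets a post-randomisation event decide where a subject and that subject's outcome are counted.

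The two tests at stake are the ones for which the plan chose ITT: superiority on moderate or greater paravalvular regurgitation at 1 year, and superiority on the effectiveness composite. Under the hierarchy in Section 12.1, the first is also the gate to the second.

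**Working it through.** **Who is affected.** Taking the rule literally in the ITT set:

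| Valves received | First valve | ITT arm under the rule | Changed? |
|---|---|---|---|
| None | – | Randomised arm | No |
| One, assigned | Assigned | Randomised arm | No |
| One, not assigned | Not assigned | Randomised arm (the rule covers only two valves) | No |
| Two | Assigned | Randomised arm | No |
| Two | The other study valve | The other arm | **Yes** |

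Only the last row moves. The third and fifth rows do not fit together: a crossover subject with one valve stays in the randomised arm, while a crossover subject who then needs a second valve is moved. Note 1 also stands under the Implanted entry of Table 26.2-1. Read literally, a subject whose second valve was the assigned one qualifies for that set but is counted in the other arm.

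**Plan's own power figures.** A two-proportion power calculation with 2:1 allocation and two-sided 0.05 gives:

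- Secondary endpoint (1.1% v 5.3%, 25% attrition): 86.4%, against about 86% stated in Section 12.1.3.2.
- Effectiveness superiority (22% v 32%, 10% attrition): 86.6%, against about 86% stated in Section 12.1.2.2.2.

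**Effect of moving one subject.** The number of such subjects is not given, so this shows sensitivity per subject and is not an estimate.

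Secondary endpoint:

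- Evaluable: 608 × 0.75 = 456 Lotus and 304 × 0.75 = 228 CoreValve.
- Expected events: 456 × 0.011 = 5.0 and 228 × 0.053 = 12.1, taken as 5 and 12.
- Difference: 12/228 − 5/456 = 5.26% − 1.10% = 4.17 points.
- Chi-square: 684 × (5 × 216 − 451 × 12)² / (456 × 228 × 17 × 667) = 10.9.
- One event moved from CoreValve to Lotus: 11/227 − 6/457 = 4.85% − 1.31% = 3.53 points, chi-square 7.8.
- Two moved the same way: 10/226 − 7/458 = 4.42% − 1.53% = 2.90 points, chi-square 5.2.
- One moved from Lotus to CoreValve: 13/229 − 4/455 = 5.68% − 0.88% = 4.80 points, chi-square 14.5.

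Effectiveness superiority:

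- Evaluable: 608 × 0.9 = 547 and 304 × 0.9 = 274. Expected events: about 120 and 88.
- Difference: 88/274 − 120/547 = 32.12% − 21.94% = 10.18 points.
- One event moved from CoreValve to Lotus: 87/273 − 121/548 = 31.87% − 22.08% = 9.79 points.

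The two-sided 5% critical value for chi-square is 3.84, so one or two moves do not overturn the secondary result at the design rates. Each does shift a test that rests on about 17 events, and the shift can favour either arm.

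**The case against.** **The rule rarely bites.** A second valve placed after the assigned valve leaves the arm unchanged. A subject must receive the other study valve first and then a second valve before anything moves. Randomised subjects must also be treatable with both devices, and the Case Review Committee confirms suitability beforehand. All of this stands, and it limits the size. It does not remove the contradiction, because the rule names all sets and is repeated inside the ITT definition.

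**The detail may lie elsewhere.** Sections 12.1.1.1 and 12.2 refer to a Statistical Analysis Plan that is not in the supplied text as a separate document. A statement there that ITT follows the randomised arm cannot be excluded. The protocol wording would still conflict with it.

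**A stronger reading.** A reader might infer that deciding both non-inferiority tests on the Implanted set alone is itself an error. The documents do not support this. The set is named consistently, ITT and as-treated analyses of the same endpoints are planned, and an Implanted set is a recognised option for non-inferiority, where untreated or crossover subjects can dilute a difference under ITT.

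The documents give no non-implantation rate by arm. The nearest anchor is REPRISE II with Lotus (Table 4.1-4): 249 of 250 as-treated (0.4% without the valve), and 247 of 250 meeting a broader delivery and deployment criterion (1.2% not meeting it). Simulation took the ITT safety difference at the 10.5-point margin and assumed 80% events in non-implanted subjects. The Implanted test declared non-inferiority in 2.5% of trials at 0.4% in each arm and 2.4% at 1.2% in each arm, against a nominal 2.5%. Inflation needs an assumed excess in the Lotus arm (3.5% at 3% Lotus v 1% CoreValve). The reverse imbalance makes the test conservative (0.7% at 1% v 5%).

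Requiring both sets to meet the margin is a trade-off. With 912 subjects and 70% events assumed in non-implanted subjects, joint effectiveness power would be 79.3% at 0.4% in each arm and 72.7% at 3% v 1%, against the stated 80%.

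**Conclusion.** Wrong as written. Applied to the ITT set, the first-valve rule moves a two-valve subject whose first valve was not the assigned one out of the randomised arm. That conflicts with intention-to-treat and with another sentence of the same definition. It reaches the secondary endpoint and the effectiveness superiority test because ITT decides both.

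The size is probably small, and it cannot be computed because no count of such subjects is given. The per-subject figures rest on the plan's design rates and attrition. A reader should not infer that the superiority tests as a whole are unreliable: single-valve crossovers and two-valve subjects whose first valve was the assigned one stay in their randomised arm.

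**What to change.** In the synopsis (Analysis Sets), Section 7, Section 12.2.1 and Table 26.2-1:

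1. Restrict the first-valve rule to the as-treated set, and remove Note 1 from the ITT and Implanted entries.
2. State that ITT subjects are analysed strictly by randomised arm, whatever valve or valves they receive.
3. If the Statistical Analysis Plan already says this, bring the protocol wording into line with it.

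The cost is wording only: no new data, no change to sample size or stated power, and no change to the deciding sets. A both-sets rule for non-inferiority is not part of this change.
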